### **7.2.2.1 Demographics**

The following demographic variables will be summarized and presented for each treatment group.

**Table 1. Demographic Variables and Analysis Methods**

Item	Classification	Testing Method
Age (at the time of Informed Consent)	Measurement value	one-way ANOVA
	<65, >= 65	-
Sex	Male, Female	chi-squared test
Height (cm)	Measurement value	one-way ANOVA
Body Weight[Screening] (kg)	Measurement value	one-way ANOVA
	<- 40 kg, 40 kg <- 60 kg, 60 kg <- 80 kg, > 80 kg	-
BMI [Screening] (kg/m2)	Measurement value	one-way ANOVA
Complications	No, Yes	
Previous Medications	No, Yes	
Concomitant Medications	No, Yes	
Concomitant DMARD except for MTX at Baseline	No, Yes	chi-squared test
Concomitant Steroid at Baseline*	No, Yes	chi-squared test
Prednisone dose at Baseline (mg/day) *	Measurement value	one-way ANOVA
	None, 0 <- 5 mg/day, > 5 mg/day	

\*: Concomitant Steroid and Prednisone dose is applied for “Oral Use”.

### 7.2.2.2 Baseline Disease Activity

The following baseline disease activity variables will be summarized by descriptive statistics, and imbalance between treatment groups will be considered based on a one-way ANOVA model with fixed effect for treatment group.

- TJC-68
- TJC-28
- SJC-66
- SJC-28
- SGAP (100 mm VAS)
- SGA (100 mm VAS)
- PGA (100 mm VAS)
- HAQ-DI (scale 0 - 3)
- CRP (mg/dL)
- ESR (mm/hr)
- DAS28-CRP
- DAS28-ESR
- SDAI score
- WPAI
- SF-36V2®

- mTSS
- Erosion Score
- Joint Space Narrowing Score
- Estimated mTSS yearly progression

Note: yearly progression from onset to baseline; baseline mTSS/ Duration of RA (years)

In addition, following baseline efficacy categorical variables will be summarized as well.

- Baseline mTSS (<=Median, > Median)
- Baseline CRP (< 1.0, >= 1.0)
- Baseline DAS28-CRP (<= 3.2, 3.2 <- 5.1, > 5.1)
- Baseline DAS28-ESR (<= 3.2, 3.2 <- 5.1, > 5.1)

All summaries will be provided separately for SAF, FAS and PPS.

### 7.2.2.3 RA History

The following RA history variables will be summarized and presented for each treatment group. All summaries will be provided separately for SAF, FAS and PPS.

**Table 2. RA History and Analysis Methods**

Item	Classification	Testing Method
ACR 1991 Revised Criteria for Global Functional Status in RA	Class I, Class II, Class III	chi-squared test
Steinbrocker Classification	Stage I, Stage II, Stage III, Stage IV	chi-squared test
Prior Surgical Procedure to Treat RA	No, Yes	chi-squared test
Duration of RA (years)	Measurement value	one-way ANOVA
	<5 years, >= 5 years	-
	< 1 year, 1 year -<5 years, 5 years -< 10 years, >- 10 years	-
Onset Age of RA (years), calculated as: (onset date of RA – date of birth+1) / 365.25	-	one-way ANOVA
Anti-CCP Antibody (U/mL)	Measurement value	one-way ANOVA
	Low-positive or negative (<- 3 x ULN), High-positive (> 3 x	-

		ULN)	
		< 4.5 U/mL, 4.5 -< 13.5 U/mL, 13.5 -< 90 U/mL, 90 -< 180 U/mL, 180 -< 500 U/mL, >- 500 U/ml	-
Rheumatoid Factor (IU/ml)		Measurement value	one-way ANOVA
		Low-positive or negative (<- 3 x ULN), High-positive (> 3 x ULN)	-
		<- 15 IU/ml, 15 <- 45 IU/ml, 45 <- 150 IU/ml, > 150 IU/ml	-
Prior MTX	Maximum Dose	Fixed Unit: mg/week	-
	Reactivity	Response, Inadequate Response, Unknown	-
	Tolerance	Intolerance, Tolerance, Unknown	-
MTX Dose at Baseline (mg/week)		Measurement value	one-way ANOVA
		0 <- 8 mg/week, 8 <- 12 mg/week, > 12 mg/week	
		0 <- 6 mg/week, 6 <- 8 mg/week, 8 <- 10 mg/week, 10 <- 12 mg/week, 12 <- 16 mg/week, 16 <- mg/week	
Prior Non-Biologic DMARD Except for MTX	Use	Non-User, User	chi-squared test
Prior Anti-TNF DMARD Use	Use	Non-User, User	chi-squared test
Prior Biologic DMARD	Use	Non-User, User	chi-squared test
Number of Prior DMARD Biologics		0, 1, 2, >= 3	chi-squared test
Number of Prior DMARDs (including biologics)		0, 1, 2, >= 3	chi-squared test
Prior Adalimumab	Use	Non-User, User	-
	Reactivity	Response , Inadequate Response, Unknown	-

	Tolerance	Intolerance, Tolerance, Unknown	-
Prior Etanercept	Use	Non-User, User	-
	Reactivity	Response, Inadequate Response, Unknown	-
	Tolerance	Intolerance, Tolerance, Unknown	-
Prior Golimumab	Use	Non-User, User	-
	Reactivity	Response, Inadequate Response, Unknown	-
	Tolerance	Intolerance, Tolerance, Unknown	-
Prior Infliximab	Use	Non-User, User	-
	Reactivity	Response, Inadequate Response, Unknown	-
	Tolerance	Intolerance, Tolerance, Unknown	-
Prior Certolizumab Pegol	Use	Non-User, User	-
	Reactivity	Response, Inadequate Response, Unknown	-
	Tolerance	Intolerance, Tolerance, Unknown	-
Prior Abatacept	Use	Non-User, User	-
	Reactivity	Response, Inadequate Response, Unknown	-
	Tolerance	Intolerance, Tolerance, Unknown	-
Prior Tocilizumab	Use	Non-User, User	-
	Reactivity	Response, Inadequate Response, Unknown	-
	Tolerance	Intolerance, Tolerance, Unknown	-
Prior Rituximab	Use	Non-User, User	-
	Reactivity	Response, Inadequate Response, Unknown	-
	Tolerance	Intolerance, Tolerance, Unknown	-
Prior Denosumab	Use	Non-User, User	-
	Reactivity	Response, Inadequate Response, Unknown	-
	Tolerance	Intolerance, Tolerance, Unknown	-

#### **7.2.2.4 Medical History**

Medical history will be coded using MedDRA/J (Version 11.1) and summarized. All summaries will be provided for SAF.

#### **7.2.3 Previous and Concomitant Medications**

Previous DMARD medications will be summarized as described in 7.2.2.3.

In addition to this, previous and concomitant medications will be coded using WHODDE(B2) (V2011SEP) and summarized by "Non-Biologic DMARD" and "previous and concomitant medications except for Non-Biologic DMARD" with preferred WHO name, respectively from following CRF page. Concomitant medications are defined as any drug medications after the first dose of study drug up to the last dose date of study drug and before the last efficacy evaluation at Week52 or Withdrawal.

[Concomitant Medication 2B -page of the CRF]

[Concomitant Medication (Non-Biologic DMARD)]

Subjects taking the same medication multiple times will be counted once per medication.

All summaries will be provided for SAF.

### **7.3 Study Drugs**

#### **7.3.1 Exposure**

The following information on drug exposure will be presented for each treatment group for the SAF and presented by overall period and treatment period up to Week 12, separately.

Duration of exposure will be summarized in two ways.

- Descriptive statistics will be presented by treatment group.
- Exposure time will be categorized according to the following categories by treatment group:

<Category for Treatment period up to Week 12>

- 1 - < 29 days
- 29 - < 57 days
- 57 - < 85 days
- 85 days -

< Category for Overall Period>

- 1 - < 85 days
- 85 - < 197 days

- 197 - < 281 days
- 281 - < 365 days
- 365 days -

Counts and percentages of subjects in each of these categories will be summarized for each treatment group for the SAF.

### 7.3.2 Treatment Compliance

Overall treatment compliance, treatment compliance during the 12 weeks of study (up to Weeks 12), treatment compliance during the 28 weeks of study (up to Weeks 28) with the dosing schedule will be examined for subjects in the SAF whose total study drug count and first and last days of treatment are known. These analyses will be summarized in two ways for the SAF:

- Descriptive statistics will be presented by Initial treatment set and 4 types of Placebo treated subjects.
- Descriptive statistics up to Week 12 will be presented by Initial treatment set. Similarly, descriptive statistics up to Week 28 will be presented by Initial treatment set.
- Percent compliance will be categorized according to the following categories by treatment group:
  - <50%
  - 50% - <75%
  - 75% - <90%
  - 90% - 100% or greater
- Percent compliance up to Week 12 will be categorized according to the following categories by treatment group. Similarly, Percent compliance up to Week 28 will be presented by Initial treatment set:
  - <50%
  - 50% - <75%
  - 75% - <90%
  - 90% - 100% or greater

For Drug Suspension and Interruption, following will be summarized.

- Experience for Drug Suspension
- Experience for Drug Interruption
- The Number of Experience for Drug Suspension per Subject
- The Number of Experience for Drug Suspension per Subject, Categorized
  - 0
  - 1
  - 2
  - $\geq 3$

- The Number of Experience Drug Interruption Per Subject, Categorized
  - 0
  - 1
  - 2

## 7.4 Analysis of Efficacy

Efficacy analysis will be conducted on FAS and PPS. The interpretation of results from statistical tests will be based on the FAS. In the primary analysis, the purpose of using PPS is to assess the robustness of the results from the statistical tests based on FAS. Efficacy analysis up to Week 12 including primary analysis will be performed by Initial Randomization Set. Efficacy analysis up to Week 52 will be performed by Treatment Sequence Set for secondary purpose. Details for analysis groups will be described in 10.1 Appendix1 and 10.2 Appendix2..

### 7.4.1 Analysis of Primary Endpoint(s)

Summary for analysis of primary endpoints are displayed at Section 10.1 Appendix 1.

#### 7.4.1.1 Primary Analysis

Primary analysis will be conducted on FAS. However, the assessment of joint destruction will be performed in subjects with at least 1 data at baseline and after Week 12. Therefore, post-baseline values for mTSS, Erosion Score, Joint Space Narrowing Score before lower allowance limit of Week 12 (Day48) will not be used for the analysis (it will be displayed in the listing).

For ACR20-CRP response at Week 12/ET, pairwise comparisons to placebo will be performed at each ASP015K dose level using Fisher's exact test in the primary analysis. For mTSS change from baseline at Week 28/ET, pairwise comparisons to placebo will be performed at each ASP015K dose level using rank analysis of covariance (RANCOVA) with treatment group (Placebo, ASP015K 100 mg, ASP015K 150 mg) as factor and baseline rank mTSS as covariate in the primary analysis.

Closed testing procedure shown below will be used for multiplicity adjustment in the primary analysis.

Four null hypotheses will be constructed:

- $H_{01}$ : ACR20-CRP response at Week 12/ET in ASP015K 150 mg is equal to that in placebo
- $H_{02}$ : ACR20-CRP response at Week 12/ET in ASP015K 100 mg is equal to that in placebo
- $H_{03}$ : mTSS change from baseline at Week 28/ET in ASP015K 150 mg is equal to that in placebo

- $H_{04}$ : mTSS change from baseline at Week 28/ET in ASP015K 100 mg is equal to that in placebo

The accompanying alternative hypotheses are:

- $H_{11}$ : ACR20-CRP response at Week 12/ET in ASP015K 150 mg is not equal to that in placebo
- $H_{12}$ : ACR20-CRP response at Week 12/ET in ASP015K 100 mg is not equal to that in placebo
- $H_{13}$ : mTSS change from baseline at Week 28/ET in ASP015K 150 mg is not equal to that in placebo
- $H_{14}$ : mTSS change from baseline at Week 28/ET in ASP015K 100 mg is not equal to that in placebo

Step 1. ACR20-CRP response at Week 12/ET: ASP015K 150 mg vs. Placebo

Step 2. ACR20-CRP response at Week 12/ET: ASP015K 100 mg vs. Placebo

Step 3. mTSS change from baseline at Week 28/ET: ASP015K 150 mg vs. Placebo

Step 4. mTSS change from baseline at Week 28/ET: ASP015K 100 mg vs. Placebo

The null hypothesis at Step 1 will be tested at a two-sided significance level of 0.05.

If it is statistically significant, the next step will be initiated and implemented in the same manner. Otherwise, it is completion of the hypothesis test. These hypothesis tests continue up to Step 4 unless it is rejected.

For each comparison, only the data for two treatment groups to be compared will be used. For the missing imputation of ACR20-CRP at Week 12/ET, Last Observation Carried Forward (LOCF) methodology will be used.

For subjects who discontinued at or before Week 28 or switched to receive ASP015K instead of placebo at Week 12 due to the lack of efficacy, mTSS at Week 28 will be extrapolated using linear extrapolation method based on the mTSS at baseline and early termination or Week 12 (before switching).

Cumulative probability plot for the change from baseline in mTSS score at Week 28/ET will be created.

#### **7.4.1.2 Sensitivity Analysis**

Multiplicity adjustment is not executed for these analyses.

##### ACR20-CRP response at Week 12/ET

In order to assess the robustness of findings from the primary efficacy analysis, the following sensitivity analyses will be performed:

- LOCF for components and NRI for response (see Section 7.11.1. for details)

- Analysis using the PPS-ACR as the analysis set with closed testing procedure  
Note: The FAS will be replaced with the PPS as analysis set, to assess robustness results from FAS.
- Observed data (data as collected, no imputation)
- Multiple Imputation, assuming Missing at Random Mechanism (see Section 7.11.1. for details)
- Placebo Multiple Imputation (pMI) (see Section 7.11.1. for details)

#### mTSS change from baseline at Week 28/ET

In order to assess the robustness of findings from the primary efficacy analysis, the following sensitivity analyses will be performed:

- Rank Analysis of Covariance with LOCF (see Section 7.11.1. for details)
- Rank Analysis of Covariance with Observed data (data as collected, no imputation)
- Rank Analysis of Covariance (LEP) using the PPS-mTSS as the analysis set with closed testing procedure
- Analysis of Covariance (ANCOVA) with treatment group (Placebo, ASP015K 100 mg, ASP015K 150 mg) and baseline mTSS as covariate. Imputation method is linear extrapolation. 95% confidence interval will be calculated.
- Analysis of Covariance (ANCOVA) with treatment group (Placebo, ASP015K 100 mg, ASP015K 150 mg) and baseline mTSS as covariate. Imputation method is Multiple Imputation (see Section 7.11.1. for details).

#### **7.4.1.3 Subgroup Analysis**

In order to evaluate homogeneity of treatment effects across subjects with different demographic and baseline characteristics, subgroup analysis of the primary efficacy variables will be performed, respectively. In addition, logistic regression model will be performed for each subgroup category and odds ratios, and 95% confidence intervals will be provided for each subgroup. The subgroups in Section 7.8 will be analyzed. As for subgroup analysis, it is not executed any statistical testing. These subgroup analyses will be displayed graphically as Dot-and-Forest plot.

#### **7.4.1.4 Adjustment for imbalances in demographics and other baseline characteristics**

As for the variables in which imbalance is present in 7.2.2, adjusted analysis will be performed to evaluate the influence.

#### ACR20-CRP response at Week 12/ET

Logistic model with each treatment group as a factor and the variables in which imbalance is present as a covariate.

#### mTSS change from baseline at Week 28/ET

Rank Analysis of Covariance (RANCOVA) with treatment group (Placebo, ASP015K 100 mg, ASP015K 150 mg) and adjusted variable (if imbalance will be detected) as factor and baseline rank mTSS as covariate.

#### **7.4.1.5 Time to the first response analysis**

Time to the first ACR20-CRP response analysis will be analyzed as following procedure. This analysis will be applied during first 12 weeks of treatment period, because placebo treated subjects can be switched to ASP015K after Week 12.

- Time to the first response analysis will be analyzed using KM profile plots for each treatment group, and log-rank test will be used for comparing each ASP015K dose group time-to-event profile versus placebo. This analysis will be applied up to Week 12.
- For each subject, time to the first event (days) will be defined as the number of days from the date of initial dose of study drug to the date the first occurrence of the event, and calculated as: date of the first occurrence of the event (most recent assessment among each components if the assessment date is different among each components) – date of initial dose of study drug +1. In addition to this, Cox proportional hazards model with a main effect for treatment group will be used comparing each ASP015K dose group versus placebo.
- Subjects who complete the treatment period through Week 12 without having the event will be censored at one day before the dosing at Week 12 day up to Day 92, and the censored time will be calculated as: one day before the dosing at Week 12 up to Day 92 – date of initial dose of study drug +1.
- In the time to response analysis, each subject will be classified as either a responder (event = 1 in time-to-event model) or a non-responder (event = 0 in time-to-event model), based on the definition in Section 6.1.1. The definition of event is the same as the definition of the binary response.
- Subjects who prematurely discontinued the treatment period through Week 12 (i.e. before the dosing at Week 12) without having the event up to Day 92 will be censored at the date of early discontinuation, and the censored time will be calculated as: date of early discontinuation from the treatment period up to Day 92 – date of initial dose of study drug +1.

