respectively. Death was reported from 1 subject of the 50 mg group (cerebral haemorrhage). AEs resulted in treatment discontinuation in 10 (17.9%), 7 (12.7%), 5 (8.8%), 6 (10.9%), and 4 (6.9%) subjects of the placebo, ASP015K 25 mg, 50 mg, 100 mg, and 150 mg groups, respectively. The most common reason was rheumatoid arthritis aggravated (21/32). Rheumatoid arthritis, nasopharyngitis, blood creatine phosphokinase (CPK) increased, diarrhoea, cystitis, constipation, stomatitis, dyspepsia, lipids increased, and blood triglycerides increased were reported at $\geq 5\%$ incidence rates from 1 or more groups. By the MedDRA System Organ Class (SOC), Infections and infestations, Gastrointestinal disorders, Musculoskeletal and connective tissue disorders, and Investigations showed high incidence rates. Blood creatine phosphokinase increased were observed in 0, 2 (3.6%), 1 (1.8%), 1 (1.8%), and 7 (12.1%) subjects of the placebo, ASP015K 25 mg, 50 mg, 100 mg, and 150 mg groups, respectively. Most cases were transient, and all subjects except 1 who prematurely discontinued the study recovered or were recovering. With regard to clinical laboratory testing, compared with the placebo group, the ASP015K groups showed decreased levels of neutrophils, platelets, and estimated glomerular filtration rate (eGFR) and elevated levels of CPK, hemoglobin, lymphocytes, creatinine, total cholesterol, LDL, HDL, and triglycerides. No noteworthy changes were detected in vital signs or ECG recordings.

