1) Subjects in the placebo group whose rate of improvement in tender and swollen joint counts is less than 20% at Week 12 will be assigned to receiving either ASP015K 100 mg or ASP015K 150 mg. Subjects will continue receiving the assigned dose thereafter.

2) Subjects in the placebo group who continued receiving placebo until the visit at Week 28 will be assigned to receiving either ASP015K 100 mg or ASP015K 150 mg. Subjects will continue receiving the assigned dose thereafter.

(2) Mode of administration

The assigned study drug will be orally administered to subjects under double-blind conditions QD after breakfast. The baseline dose should be given at each study center on the day of the baseline visit after all assessments and tests are completed.

Doses on the day of scheduled visits during the treatment period should be given on the day of the visit after all assessments and tests are completed, except for blood sampling for the assessment of post-dose concentrations.

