On this assumption, the necessary sample size was calculated to enable to analyze ACR20 using the Fisher's exact test and the change in mTSS at Week 28 using the t-test. When a closed testing procedure (in Section 7.4.1.1 Primary Analysis) considering multiplicity is used in the primary analysis, the sample size needed to verify the hypotheses Step 1 through Step 3 at a 2-sided 5% significance level with 90% power is 151 subjects per group. By considering about 10% drop-out, this study will enroll 170 patients in each treatment group. Moreover, from the long term safety point of view, this sample size is also needed to keep 300 subjects for 6 month period, 100 subjects for 1 year period in both ASP015K 100 mg and 150 mg among RAJ2/RAJ3/RAJ4 studies.

- CONFIDENTIAL -

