## 7 STATISTICAL METHODOLOGY

### 7.1 General Considerations

- For continuous variables, descriptive statistics will include the number of subjects (n), mean, standard deviation (SD), median, minimum, and maximum.
- For categorical variables: number and percentages of subjects will be described.
- For time-to-event variables: number and percentage of subjects with the event using Kaplan-Meier method, the cumulative event rate will be estimated and a plot will be constructed.
- All data processing, summarization, and analyses will be performed using SAS Drug Development (ver. 4.5), and PC-SAS (ver. 9.4) or higher versions.
- Specifications for table, figures, and data listing formats can be found in the TLF specifications for this study.

- For the definition of subgroups of interest can be referred to section [7.8](#)
- Summaries based on FAS and PPS (e.g. disposition, baseline and efficacy data) will be presented by actual treatment groups, unless specifically stated otherwise. Safety analysis and other summaries based on SAF will also be presented by actual treatment groups.
- Initial Randomization Set of efficacy analyses except for mTSS, erosion score, and joint space narrowing score are those of the efficacy data up to Week 12 and include the primary analysis (ACR20 at Week 12/ET) as described 7.4.1.1. This set will be analyzed by the initially treated groups (ASP015K 100 mg, ASP015K 150 mg, and Placebo) and statistical testing will be performed for ASP015K 100 mg, and 150 mg, compared with Placebo. In addition, statistical testing will also be conducted at Week 28/ET.

Table 3 Initial Randomization Set

Initial Randomization Arm Code	Initial Randomization Label	Analysis Scope
PLACEBO	Placebo	Screening, Week 0 to Week 12, Week 12/ET, Week 28/ET
100MG	100 mg	
150MG	150 mg	

- Treatment Sequence Set of efficacy analyses except mTSS, erosion score, and joint space narrowing score are those of the efficacy data up to Week 52. Taking into consideration a switch from placebo to active treatment at Week 12 or Week 28, this set will be analyzed by following groups defined below. The four types of "Placebo to ASP015K xx mg at Week xx" groups are not for primary objective and are conducted optionally for efficacy and safety.

Table 4 Treatment Sequence Set

Treatment Sequence Code	Treatment Sequence Label	Week0- Week12	Week 12- Week 28	Week 28- Week 52	Analysis Scope
SEQ1	100mg,	ASP015K 100 mg	ASP015K 100 mg	ASP015K 100 mg	Screening, Week 0 to Week 52, EOT

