#### **7.4.2 Analysis of Secondary Endpoints**

Refer to Section 10.2 Appendix 2. They include categorical, continuous, and time-to-event variables, with "X" indicating that the variable will be analyzed. As for secondary variables, no multiplicity adjustment will be done. Basically, analysis of secondary endpoints except for mTSS, erosion score, and joint space narrowing score will be performed by Initial Randomization Set and Treatment Sequence Set defined at Section 7.1.

The secondary variables and analyses are as follows:

<Initial Randomization Set>

- Categorical variables at each visit (including Baseline, Weeks 4, 8, 12, 12/ET, Week 28/ET) will be analyzed using Fisher's exact test, as described for the primary efficacy variable, unless otherwise specified in Section 10.2 Appendix 2.
- Raw value and change from baseline variables at each visit (Baseline, Weeks 4, 8, 12, 12/ET, Week 28/ET) will be analyzed using the ANCOVA model with fixed effects for treatment, and baseline value as a covariate.
- Time to the first response analysis will be analyzed similarly as described in 7.4.1.5.
  - ACR50-CRP
  - ACR70-CRP
  - DAS28-CRP <2.6
  - SDAI score <= 3.3
  - CDAI score <= 2.8
  - ACR/EULAR score for remission

As for DAS28-CRP < 2.6, CDAI score <= 2.8, SDAI score <= 3.3, ACR/EULAR score for remission, if the event is occurred at baseline, then that subject is excluded from this analysis.

- Graphical analysis (including Baseline, Weeks 4, 8, 12, 12/ET, Week 28/ET).
  - ACR20/50/70-CRP will be plotted for over time.
  - The mean-standard deviation plot of actual values and changes from baseline will be presented for DAS28-CRP and DAS28-ESR.
  - To visually explore possible relationships between ACR20-CRP and DAS28-CRP, 2-panel line graphs of DAS28-CRP over time will be plotted for ACR20-CRP responders (in 1 panel) and non-responders (in another panel). Similar graphs will be provided for DAS28-ESR.

<Treatment Sequence Set>

- Categorical variables at each visit (including Baseline, Weeks 4, 8, 12, 16, 20, 24, 28, 32, 36, 40, 44, 48, 52, EOT) will be summarized as described in Section 10.2 Appendix 2.
- Raw value and change from baseline variables at each visit (including Baseline, Weeks 4, 8, 12, 16, 20, 24, 28, 32, 36, 40, 44, 48, 52, EOT) will be summarized by descriptive statistics.
- Graphical analysis (including Baseline, Weeks 4, 8, 12, 16, 20, 24, 28, 32, 36, 40, 44, 48, 52, EOT).
  - ACR20/50/70-CRP will be plotted for over time.

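### Censoring non-responders at discontinuation makes the Kaplan-Meier cumulative event rate overstate the proportion of treated patients who ever respond by Week 12.

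*SAP*

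**What the plan says.** SAP 7.4.1.5 defines time to first ACR20-CRP response over the first 12 weeks, with Kaplan-Meier plots, a log-rank test and a Cox model. Patients who discontinue before the Week 12 dose "without having the event up to Day 92 will be censored at the date of early discontinuation". Patients who complete Week 12 without a response "will be censored at one day before the dosing at Week 12 day up to Day 92".

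SAP 7.1 sets out what analyses of this kind will report: "number and percentage of subjects with the event using Kaplan-Meier method, the cumulative event rate will be estimated and a plot will be constructed". No cumulative-incidence or competing-event method is planned.

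SAP 7.4.2 extends the method to ACR50, ACR70, DAS28-CRP <2.6, SDAI, CDAI and ACR/EULAR remission: "Time to the first response analysis will be analyzed similarly as described in 7.4.1.5". Appendix 2 lists Kaplan-Meier only for ACR20/50/70 and DAS28-CRP <2.6. The other three have Cox and log-rank only.

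**The concern.** Kaplan-Meier censoring assumes that a censored patient would have gone on to respond at the same rate as those still followed. A patient who stops treatment without a response has an early-termination and a follow-up visit and then leaves, so a later first response on assigned treatment is no longer possible. Discontinuation without response is a competing event.

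The documents also tie discontinuation to non-response:

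- Protocol 3.4, criterion 2, is discontinuation because the drug is not effective enough.
- In the Phase IIb study (Protocol 1.3), "AEs resulted in treatment discontinuation in 10 (17.9%), 7 (12.7%), 5 (8.8%), 6 (10.9%), and 4 (6.9%) subjects" (placebo, 25, 50, 100 and 150 mg), and 21 of those 32 were for aggravated rheumatoid arthritis.

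The binary ACR20 analysis treats these patients differently. LOCF keeps them in the denominator with their last status, although SAP 7.4.1.5 says that the event definition is the same as for the binary response. At stake is a plotted and tabulated rate that readers will take as the share of patients who responded.

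**Working it through.** **Plan's own figure.** The SAP gives none for this analysis. Its sample size reproduces: 0.5 against 2.0 with SD 4.0, two-sided 5% and 90% power, gives 151 per group by the exact t calculation (power 90.1%). The drop-out allowance then gives 151/0.9 = 167.8, so 168, against 170 planned. No period is attached to it.

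**Inputs.** ACR20 rates of 25%, 54.5% and 65.5% (SAP 4) are used as the assumed true proportions ever responding by Week 12. Visits are at Days 29, 57 and 85. Discontinuation without response before Week 12 is assumed at 5%, 10%, or the Phase IIb AE rates (17.9% placebo, 10.9% 100 mg, 6.9% 150 mg).

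**Formula.** At visit k, with r_k the fraction first responding and n_k = 1 − earlier responders − discontinuers so far, the reported rate is 1 − Π(1 − r_k/n_k). The true proportion is Σ r_k.

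**Worked case.** 150 mg, 10% drop-out spread evenly before the three visits, responses split 40/35/25, completers kept at risk through Week 12:

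| Visit | n_k | r_k | 1 − r_k/n_k |
|---|---|---|---|
| Day 29 | 1 − 0.0333 = 0.9667 | 0.2620 | 0.7290 |
| Day 57 | 0.9667 − 0.2620 − 0.0333 = 0.6713 | 0.2293 | 0.6585 |
| Day 85 | 0.6713 − 0.2293 − 0.0333 = 0.4088 | 0.1638 | 0.5994 |

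The product is 0.2877, so the reported rate is 71.2% against a true 65.5%. The same steps give 26.8% against 25% for placebo and 59.0% against 54.5% for 100 mg.

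**Range.** Responses and drop-outs are each split equally, 50/30/20 or 20/30/50 over the visits. Entries are the overstatement in points.

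| Drop-out | Placebo | 100 mg | 150 mg | 150 mg − placebo (true 40.5) |
|---|---|---|---|---|
| 5% each arm | 0.6–1.1 | 1.7–2.6 | 2.2–3.2 | 42.1–42.6 |
| 10% each arm | 1.4–2.4 | 3.6–5.5 | 4.8–6.8 | 43.9–44.9 |
| Phase IIb rates | 2.6–4.7 | 4.0–6.1 | 3.2–4.5 | 40.3–41.1 |

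The sign is positive throughout. For a rare endpoint the gap shrinks: at 10% drop-out it is about 0.7 point at 10% response and 0.3 point at 5%.

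**Interaction with the completer rule.** Visit-day doses "should be given on the day of the visit after all assessments and tests are completed" (Protocol 5.1.1), so a Week 12 response is dated at the visit, while a non-responding completer is censored the day before. I simulated 170 per arm with 10% drop-out (Days 2 to 77) and responses split 40/35/25. Where visits vary, each patient's visits shift together by up to 7 days. Percentages are placebo/100 mg/150 mg; the true values are 25/54.5/65.5.

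| Completers censored | Visits | Discontinuers censored when they stop, 1 − KM | Discontinuers kept to Day 92, 1 − KM | Aalen-Johansen |
|---|---|---|---|---|
| Day before Week 12 dose (SAP) | all Day 85 | 100/100/100 | 49/75/81 | 90/90/90 |
| Day before Week 12 dose (SAP) | ±7 days | 71/96/98 | 34/65/74 | 64/86/88 |
| Own Week 12 visit day | ±7 days | 40/79/89 | 32/63/73 | 37/72/81 |
| Day 92 | ±7 days | 27/59/71 | 25/54/65 | 25/54/65 |

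The two remedies for discontinuers agree with each other and with the truth only when completers also stay at risk to a common end such as Day 92. Censoring each completer on the day of the visit is enough only if all visits fall on the same day.

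**The case against.** The strongest objection is that the completer rule in the same section swamps this effect. That stands. The excess of 1 to 7 points is what discontinuer censoring adds once completers are handled properly. It is not what the SAP as written would print, and repairing the discontinuers alone would not recover the true rates.

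The size is also assumed. The sentence "By considering about 10% drop-out, this study will enroll 170 patients in each treatment group" has no stated period and inflates a number set by the Week 28 mTSS test, so a reader should not take 10% as the loss by Week 12. The Phase IIb rates cover AE discontinuations only and come from single-agent therapy, without the MTX background used here. The calculation further assumes that everyone who leaves does so before responding.

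One-minus-Kaplan-Meier would be defensible for a different target, response had nobody discontinued, under independent censoring. The SAP states no such target, and the Phase IIb reasons for stopping argue against independence. SAP 7.1 also mentions the number and percentage with the event, which might mean the crude proportion, but its wording ties this to Kaplan-Meier.

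Three stronger readings are tempting and not supported:

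- **The curve should match the Week 12/ET rate.** It need not, even when corrected, because a first response can later be lost.
- **The treatment comparison is distorted.** At the Phase IIb rates the difference hardly moves, and log-rank and Cox can be read with discontinuers censored, as cause-specific on-treatment comparisons.
- **All seven endpoints are affected.** Appendix 2 plans Kaplan-Meier for four.

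**Conclusion.** The point holds as a flaw in how a supportive, multiplicity-unadjusted analysis is estimated. Given completers kept at risk through Week 12, the direction is certain: the Kaplan-Meier rate exceeds the proportion of treated patients who ever respond by Week 12 in any arm where a non-responder discontinues before a later response. The size rests on the drop-out and timing assumptions above, and on using the SAP's ACR20 rates as ever-response rates. The shift in the 150 mg-placebo difference depends on how drop-out falls across arms: under 1 point at the Phase IIb rates, and 3.4 to 4.4 points (43.9 to 44.9 less 40.5) if 10% leave every arm. The primary Fisher test does not use this censoring. The change is worth making because it is cheap and the error runs one way.

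**What to change.** 1. In SAP 7.1 and 7.4.1.5, for the plotted and tabulated cumulative rates of ACR20/50/70 and DAS28-CRP <2.6, report the Aalen-Johansen cumulative incidence with discontinuation without response as a competing event. Alternatively, keep such patients at risk as non-responders to Day 92.
2. In the same amendment, censor non-responding completers at Day 92, or use nominal visit times, so that they are at risk whenever a Week 12 response is counted. Without this, neither option in item 1 recovers the true rate and the two are not equivalent.
3. Keep censoring at discontinuation only for the log-rank and Cox tests, and label them as cause-specific on-treatment comparisons. The completer change in item 2 should apply to them too.
4. Add a note that the curve shows first response and need not equal the Week 12/ET rate.

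The cost is a few sentences in the SAP and changed censoring dates or an added estimator in the program. No data collection, endpoint or alpha changes. The reported cumulative response rates become lower.
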